Period	A subdivision of the study timeline; divides stages into smaller functional segments such as screening, baseline, titration, washout, etc.
Personal data	Subject information collected by the Investigator that is transferred to Novartis for the purpose of the clinical trial. This data includes patient identifier information, study information and biological samples.
Randomization number	A unique treatment identification code assigned to each randomized patient, corresponding to a specific treatment arm assignment
Stage related to study timeline	A major subdivision of the study timeline; begins and ends with major study milestones such as enrollment, randomization, completion of treatment, etc.
Stage in cancer	The extent of a cancer in the body. Staging is usually based on the size of the tumor, whether lymph nodes contain cancer, and whether the cancer has spread from the original site to other parts of the body
Stop study participation	Point/time at which the patient came in for a final evaluation visit or when study treatment was discontinued whichever is later
Study treatment	Includes any drug or combination of drugs in any study arm administered to the patient (subject) as part of the required study procedures, including placebo and active drug run-ins. In specific examples, it is important to judge investigational treatment component relationship relative to a study treatment combination; study treatment in this case refers to the investigational and non-investigational treatments in combination.
Study treatment interruption	Includes any delay or withholding of study treatment for any reason as well as an interruption during an infusion of study treatment for any reason
Study treatment discontinuation	Point/time when patient permanently stops taking study treatment for any reason
Treatment group	A treatment group defines the dose and regimen or the combination, and may consist of 1 or more cohorts. Cohorts are not expanded, new cohorts are enrolled.

Variable	Identifier used in the data analysis; derived directly or indirectly from data collected using specified assessments at specified time points
Withdrawal of study consent	Withdrawal of consent from the study occurs only when a subject does not want to participate in the study any longer, and does not allow any further collection of personal data

Amendment 7 (27-Jan-2023)

Amendment rationale

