Trial participants who have been exposed to someone infected by COVID-19 and/or who develop symptoms indicative of potential COVID-19 infection (see above) should contact the Investigator and discuss the next steps; these may include self-quarantine, or may require further testing/follow-up as appropriate. Administration of the study treatment may be delayed based on the risk benefit assessment until the trial participant completes the quarantine and remains asymptomatic and/or COVID-19 infection has been ruled out. Investigators are recommended to follow the local health authority guidelines for prevention against COVID-19.

[figure not shown]
[figure not shown]

Table 6-7 Dose modification steps for PDR001/placebo, dabrafenib and trametinib

Dose modification for PDR001 or placebo ^a				
	Starting dose level	Dose level - 1		
PDR001 or placebo	400 mg Q4W 400 mg Q8W (only if DL-1a is determined to be the dose regimen)	Not applicable		
Dose reduction for dabrafenib ^{a, b}				
	Starting dose level	Dose level - 1	Dose level - 2	Dose level - 3
Dabrafenib	150 mg BID (300 mg/day)	100 mg BID (200 mg/day)	75 mg BID (150 mg/day)	50 mg BID (100 mg/day)
Dose reduction for trametinib ^{a, b}				
	Starting dose level	Dose level - 1	Dose level - 2	Dose level - 3
Trametinib	2 mg QD	1.5 mg QD	1.0 mg QD	-
Q4W: once in every 4 weeks; BID: twice daily; QD: once daily				
^a . Dose modification should be based on the worst toxicity demonstrated at the last dose.				
^b . Dose reduction below 50 mg BID for dabrafenib and 1.0 mg QD for trametinib are not allowed.				

Table 6-8 Reference of AEs and toxicity management guidelines

Adverse Events	PDR001	dabrafenib	trametinib	Guideline
Diarrhea/colitis	X	X	X	Section 6.3.3.1 Table 6-9.
Abnormal liver enzyme test	X	X	X	Section 6.3.3.2 Table 6-10.
Skin rash	X	X	X	Section 6.3.3.3 Table 6-11.
Serious skin reaction	X	X	X	Section 6.3.3.4
Nephritis	X	X	X	Section 6.3.3.5 Table 6-12
Pneumonitis	X	X	X	Section 6.3.3.6 Table 6-13
Encephalitis	X	X	X	Section 6.3.3.7 Table 6-14
Endocrine events	X	X	X	Section 6.3.3.8 Table 6-15
Hand foot skin reaction	X	X	X	Section 6.3.3.9 Table 6-16
Neutropenia and thrombocytopenia	X	X	X	Section 6.3.3.10 Table 6-17
Adverse events including abnormal laboratory related AEs	X	X	X	Section 6.3.3.11 Table 6-18
Asymptomatic amylase and/or lipase elevation	X	X	X	Section 6.3.3.11 Table 6-18
Others	X	X	X	Section 6.3.3.12 Table 6-19
Infusion reaction and cytokine release syndrome	X			Section 6.3.4 Table 6-20

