	
(Infliximab is contraindicated in subjects with sepsis or a perforation). Upon symptomatic relief initiate a prolonged steroid taper over 45 to 60 days.
 
 If symptoms worsen during steroid reduction, initiate a re-tapering of steroids starting at a higher dose followed by a more prolonged taper and administer infliximab. If symptoms persist despite the above treatment, a surgical consult should be obtained. 	
 Permanently discontinue dabrafenib and trametinib.
Grade 4: Life-threatening consequences; urgent intervention indicated	
 Same as Grade 3 	
 Permanently discontinue PDR001/placebo, dabrafenib and trametinib.

6.3.3.2 Mandatory dose modifications and recommended clinical management guidelines for abnormal liver enzyme test

Guidelines for dose modification and management of abnormal liver enzyme functions considered to be related to study treatment by the investigator are provided in [Table 6-10](#).

In addition to the instructions below, subjects with normal baseline transaminases and bilirubin who experience sudden elevations even within Grade 1, should be monitored more closely.

Table 6-10 Mandatory dose modifications and recommended clinical management guidelines for abnormal liver enzyme test

Abnormal liver enzyme tests/hepatitis		
Grade	Recommended adverse event management guidelines	Mandatory dose modification requirements
Grade 2: AST or ALT >3× ULN to ≤ 5× ULN and/or bilirubin > 1.5× ULN to ≤ 3× ULN	
 Monitor hepatic laboratory tests more frequently (every 2-3 days) until returned to baseline values 	
 Interrupt PDR001/placebo, dabrafenib and trametinib until ≤ Grade 1, and then reinstate PDR001/placebo, dabrafenib and trametinib at the same dose level.

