Grade 3 or 4: AST or ALT > 5× ULN and/or bilirubin > 3× ULN	
 Monitor hepatic laboratory tests more frequently (every 2-3 days) until return to baseline values. Consider appropriate consultation* with hepatologist and liver biopsy to establish etiology of hepatic injury, if necessary If after 2-3 days new liver assessment shows worsening of laboratory test consider to initiate treatment with high dose steroids (1 to 2 mg/kg/day prednisone or equivalents) 	
 Permanently discontinue PDR001/placebo only if causality is suspected to be related to PDR001/placebo ** If lab results show worsening, follow the management and dose modification (instructions below) 
1st occurrence
 
 Interrupt dabrafenib and trametinib until recovery to ≤ Grade 1 or baseline 
 Reduce dabrafenib and trametinib to the next lower dose level per Table 6-7. Re-escalation of the subject's

Abnormal liver enzyme tests/hepatitis

Grade	Recommended adverse event management guidelines	Mandatory dose modification requirements
	
 Add prophylactic antibiotics for opportunistic infections Start steroid taper as outlined in Section 6.3.4.1 if symptoms improve to Grade ≤ 1 If serum transaminase levels do not decrease 48 hours after initiation of systemic steroids, oral mycophenolate mofetil 500 mg every 12 hours may be given. Infliximab is not recommended due to its potential for hepatotoxicity 	
dose is recommended if criteria in Section 6.3.2 are met.
 
 If no recovery to \leq Grade 2 within 10 weeks, permanently discontinue dabrafenib and trametinib. 
2nd occurrence
 
 Interrupt dabrafenib and trametinib until \leq Grade 1. Reduce dabrafenib and trametinib to the next lower dose level per Table 6-7. Re-escalation of the subject's dose is recommended if criteria in Section 6.3.2 are met. 
3rd occurrence
 
 Permanently discontinue dabrafenib and trametinib

*Rule out viral hepatitis and other potential causes of liver injury

**For patients with liver metastasis who begin treatment with Grade 2 AST or ALT, if AST or ALT increase by $\geq 50\%$ relative to baseline and last for at least 1 week then the patient should be discontinued

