Note: For additional information on follow-up of potential drug induced liver injury cases, refer to [Section 6.3.6.2](#).

[figure not shown]

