6.3.6.2 Follow up on potential drug-induced liver injury (DILI) cases

[figure not shown]
Subjects with transaminase increase combined with an elevation of total bilirubin (TBIL) may be indicative of potential DILI; these events should be considered as clinically important.

The threshold for potential DILI may depend on the subject's baseline AST/ALT and TBIL value; subjects meeting any of the following criteria will require further follow-up as outlined below:

- For subjects with normal ALT and AST and TBIL value at baseline: AST or ALT > 3.0 x ULN combined with TBIL > 2.0 x ULN
- For subjects with elevated AST or ALT or TBIL value at baseline: [AST or ALT > 2 x baseline AND > 3.0 x ULN] OR [AST or ALT > 8.0 x ULN], combined with [TBIL > 2 x baseline AND > 2.0 x ULN]

Medical review needs to ensure that liver test elevations are not caused by cholestasis, defined as ALP elevation > 2.0 x ULN with R value < 2 in subjects without bone metastasis, or elevation of ALP liver fraction in subjects with bone metastasis.

Note: (The R value is calculated by dividing the ALT by the ALP, using multiples of the ULN for both values. It denotes whether the relative pattern of ALT and/or ALP elevation is due to cholestatic ($R \leq 2$), hepatocellular ($R \geq 5$), or mixed ($R > 2$ and < 5) liver injury).

In the absence of cholestasis, these subjects should be immediately discontinued from study drug treatment, and repeat LFT testing as soon as possible, preferably within 48 hours from the awareness of the abnormal results. The evaluation should include laboratory tests, detailed history, physical assessment and the possibility of liver metastasis or new liver lesions, obstructions/compressions, etc.

1. Laboratory tests should include ALT, AST, albumin, creatine kinase, total bilirubin, direct and indirect bilirubin, GGT, prothrombin time (PT)/INR and alkaline phosphatase.
2. A detailed history, including relevant information, such as review of ethanol, concomitant medications, herbal remedies, supplement consumption, history of any pre-existing liver conditions or risk factors, should be collected.
3. Further testing for acute hepatitis A, B, C or E infection and liver imaging (e.g., biliary tract) may be warranted.
4. Additional testing for other hepatotropic viral infection (e.g., CMV, EBV, Adenovirus, HSV, HHV6, HIV), autoimmune hepatitis or liver biopsy may be considered as clinically indicated or after consultation with specialist/hepatologist.

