All cases confirmed on repeat testing meeting the laboratory criteria defined above, with no other alternative cause for LFT abnormalities identified should be considered as “medically significant”, thus, met the definition of SAE ([Section 8.2.1](#)) and reported as SAE using the term “potential drug-induced liver injury”. All events should be followed up with the outcome clearly documented.

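### For the same potential drug-induced liver injury case, Section 6.3.6.2 discontinues study drug with no restart rule, while the Table 6-10 Grade 2 row restarts all study drugs at the same dose level after recovery

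*Protocol*

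**What the plan says.** Section 6.3.6.2 sets laboratory criteria for potential drug-induced liver injury (DILI) and, once cholestasis is excluded, directs: "In the absence of cholestasis, these subjects should be immediately discontinued from study drug treatment, and repeat LFT testing as soon as possible". It then lists the work-up. "All cases confirmed on repeat testing meeting the laboratory criteria defined above, with no other alternative cause for LFT abnormalities identified" are to be reported as serious adverse events and followed to outcome. The section does not say whether or when drug may resume. The glossary entry for study treatment discontinuation reads "Point/time when patient permanently stops taking study treatment for any reason", and interruption has its own entry.

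Table 6-10 in Section 6.3.3.2 covers "abnormal liver enzyme functions considered to be related to study treatment by the investigator". Its Grade 2 row is AST or ALT above 3 and up to 5 x ULN, bilirubin above 1.5 and up to 3 x ULN, or both. The mandatory column interrupts all three drugs until Grade 1 or lower, "and then reinstate PDR001/placebo, dabrafenib and trametinib at the same dose level". The Grade 3 or 4 row says "Permanently discontinue PDR001/placebo only if causality is suspected to be related to PDR001/placebo", and restarts dabrafenib and trametinib one dose level lower after a first or second occurrence.

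A note under the table says "For additional information on follow-up of potential drug induced liver injury cases, refer to" Section 6.3.6.2. The abnormal liver enzyme row of Table 6-8 names only "Section 6.3.3.2 Table 6-10".

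**The concern.** A combined rise in transaminases and bilirubin without cholestasis is the pattern that Section 6.3.6.2 singles out as clinically important. The Grade 2 row of Table 6-10 also takes in combined rises, because its two laboratory ranges are joined by and/or. One subject can therefore fall under both rules. After recovery, a site following the mandatory column restarts study drug at the same dose level. A site following Section 6.3.6.2, read with the glossary, does not restart. At stake is re-exposure of a subject with potential drug-induced liver injury, decided by which page the site reads.

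**Working it through.** The protocol gives no figure to reproduce. The check intersects the two laboratory ranges and then compares the required actions. All values are multiples of ULN unless stated.

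**1. Normal baseline ALT, AST and bilirubin.** Section 6.3.6.2 requires AST or ALT > 3 with TBIL > 2. The Grade 2 row covers AST or ALT in (3, 5] and/or bilirubin in (1.5, 3].

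- AST/ALT: (3, ∞) ∩ (3, 5] = (3, 5]
- TBIL: (2, ∞) ∩ (1.5, 3] = (2, 3]

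The overlap is not empty.

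**2. Elevated baseline B.** Section 6.3.6.2 then also requires each value to exceed 2 × B. The lower limits become max(3, 2B) for AST/ALT and max(2, 2B) for TBIL. The alternative limb, AST/ALT > 8, lies outside the Grade 2 row.

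| Baseline AST/ALT | Overlap | Baseline TBIL | Overlap |
|---|---|---|---|
| 1.5 | > 3 to 5 | 1.0 | > 2 to 3 |
| 2.0 | > 4 to 5 | 1.2 | > 2.4 to 3 |
| 2.4 | > 4.8 to 5 | 1.4 | > 2.8 to 3 |
| 2.5 | none | 1.5 | none |

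The AST/ALT baseline is that of the enzyme meeting the DILI criterion. Inclusion criterion 13 (Section 5.2.4) admits AST and ALT below 2.5 and bilirubin up to 1.5, apart from subjects with liver metastasis or Gilbert's syndrome. Outside those exceptions, some overlap remains for nearly every admissible baseline.

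**3. Cholestasis exclusion, no bone metastasis.** Cholestasis is ALP > 2 with R = ALT/ALP < 2. R < 2 means ALP > ALT/2, so a case is non-cholestatic when ALP ≤ max(2, ALT/2). The ceiling is 2.0 for ALT up to 4, 2.25 at ALT 4.5 and 2.5 at ALT 5. The exclusion does not empty the overlap.

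**4. Example.** Normal baseline, ALT 4, TBIL 2.5, ALP 1.5. R = 4/1.5 = 2.67 and ALP is not above 2, so the case is not cholestatic. Section 6.3.6.2 discontinues it. If it is considered related to treatment, Table 6-10 also applies. After recovery, the Grade 2 row returns dabrafenib at 150 mg BID and trametinib at 2 mg QD in a subject with no earlier reduction, or 100 mg BID and 1.5 mg QD in one already at level -1 (Table 6-7).

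**5. Actions side by side.**

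| | Section 6.3.6.2 | Table 6-10, Grade 2 row |
|---|---|---|
| At onset | Stop study drug | Interrupt all three drugs |
| After recovery to ≤ Grade 1 | No restart rule; permanent stop by the glossary | Restart all three at the same dose level |
| Limit on repeat occurrences | Not addressed | None stated |

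The rules agree at onset and part at recovery.

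**6. Precedence.** The note under Table 6-10 points to Section 6.3.6.2 for follow-up information and makes no exception to the dose column. Section 6.3.6.2 says should, whereas the table column is headed mandatory. Table 6-10 does carry an explicit discontinuation footnote for subjects with liver metastasis and Grade 2 AST or ALT at baseline, but none for combined elevation.

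**7. Above the Grade 2 row.** With AST/ALT > 5 or bilirubin > 3, the conflict is narrower: the table stops PDR001 if it is suspected and restarts dabrafenib and trametinib at a reduced dose.

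**8. Exposed subjects.** The Amendment 7 rationale gives 2 + 1 + 88 = 91 subjects on treatment. Placebo had stopped and PDR001 continuation was case by case (Section 6.5.3), so the number still on PDR001 is not given and some of the 91 would restart two drugs, not three.

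**The case against.** The best reply is that discontinued in Section 6.3.6.2 means stop and investigate. The same sentence asks for prompt repeat testing, and the dose tables usually add permanently when they mean it. The glossary term is also not word for word the phrase used in Section 6.3.6.2. This is a possible reading, but it does not close the gap. Section 6.3.6.2 attaches only reporting and follow-up to a confirmed case with no alternative cause. The one written restart rule is then the Grade 2 row, at the same dose level.

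A second reply is that the DILI rule is the more specific and naturally prevails, and that the note under the table leads sites to it. That is sensible, but the protocol does not say so.

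A third reply stands in part. Restart requires recovery. Section 6.3.2 ends dabrafenib and trametinib if an event related to them has not recovered within 4 weeks, and Section 6.3.1 ends PDR001 after 12 weeks without recovery from a related event. Section 6.1.5 lists unacceptable toxicity and investigator discretion as grounds for stopping, and after the final PFS analysis makes continuation of the triplet an individual benefit-risk decision. A reader might infer that sites are compelled to rechallenge a confirmed case, or that subjects stay on drug during the injury. The documents support neither: both rules stop drug at once, and an investigator may decline to restart. These safeguards limit the conflict but do not say which rule governs a subject who recovers.

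**Conclusion.** The inconsistency is real and limited to restart. It covers treatment-related, non-cholestatic events with AST/ALT above 3 and up to 5 x ULN and TBIL above 2 and up to 3 x ULN when baseline liver tests are normal, and a narrower range otherwise. It matters for subjects who recover within the limits of Sections 6.3.1 and 6.3.2. It should be fixed because following the table's mandatory column returns a potential drug-induced liver injury case, even a confirmed one, to the same dose level.

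A reader might infer a bias in the PFS or OS comparison, or a known number of affected subjects. Neither is supported: no event frequency is given, and the 91 is only a denominator. The remaining in-study exposure is also short. The last randomized subject was first treated in July 2018, and the 5-year follow-up ends about half a year after Amendment 7 (January 2023).

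The conclusion assumes that no precedence or restart rule stands in the sections not seen, notably Section 7.1.4 on discontinuation of study treatment.

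**What to change.** In the mandatory dose-modification column only, in both rows of Table 6-10, add: *Cases meeting the Section 6.3.6.2 criteria without cholestasis follow the treatment rule in Section 6.3.6.2.* Leave the recommended-management column in force. It holds the closer monitoring and, for Grade 3 or 4, the steroid and mycophenolate guidance, which Section 6.3.6.2 does not contain.

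In Section 6.3.6.2, state three things:

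- PDR001/placebo, dabrafenib and trametinib are all stopped at once pending repeat testing and work-up.
- All are permanently discontinued if the case is confirmed with no alternative cause.
- Restart, on the terms of Table 6-10, is allowed only if an alternative cause is found.

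Section 6.3.5.9 already uses the same two steps for hemophagocytic lymphohistiocytosis: interrupt on suspicion, stop permanently on confirmation.

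The cost is a short protocol amendment with IRB/IEC approval and a site letter. Amendment 7, which changed similar dose rules, needed that approval before implementation. No data collection or analysis changes.

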6.4 Concomitant medications

The investigator must instruct the subject to notify the study site of any new medication(s) he/she takes after start of study participation. All prescription medications, OTC drugs and significant non-drug therapies (including physical therapy, herbal/natural medications and blood transfusions) taken within 28 days or 5 half-lives, whichever is shorter, including vitamins taken within one week prior to dosing must be recorded on the ‘Prior and Concomitant Medications’ or ‘Surgical and Medical Procedures’ eCRF. Prior antineoplastic therapies including medications, radiotherapy, and surgery are to be recorded on the separate ‘Prior Antineoplastic Therapy eCRF’ page during screening. Medication entries must be specific to trade name, dose and units, frequency and route of administration, start and discontinuation dates, and reason for therapy. For medications administered one time, the frequency column may reflect “once”.

Administration of certain concomitant medications may lead to the requirement for subject to be discontinued. Discussions regarding discontinuation of subjects requiring concomitant medication will be discussed with Novartis on a case by case

6.4.1 Permitted concomitant therapy

In general, concomitant medications and therapies deemed necessary for the supportive care (e.g., such as anti-emetics, anti-diarrhea) and safety of the subject are allowed except those prohibited in [Section 6.4.3](#).

Subjects are permitted to use the following medications during study treatment:

- Antivirus medications to manage HBV or HCV infection and/or prevent reactivation (e.g., tenofovir); supportive care.
- Medications to prevent or treat nausea or vomiting.
- Anti-diarrheal medications (e.g., loperamide) for subjects who develop diarrhea.
- Pain medication to allow the subject to be as comfortable as possible.
- Bone targeted therapies (e.g., bisphosphonates, denosumab) to treat bone metastases or to prevent skeletal related events.
- Any radiotherapy must be listed on the ‘Concomitant Antineoplastic Therapy - Radiotherapy’ eCRF.
- Immunosuppressive agents to treat suspected irAEs.
- Nutritional support or appetite stimulants (e.g., megestrol).
- Oxygen therapy and blood products or transfusions.
- Limited-field palliative radiotherapy to non-target lesion(s) may be allowed after documented discussion with Novartis study physician as concomitant therapy such as local therapies administered during the study treatment. In case of palliative radiotherapy, the subject should interrupt dabrafenib and trametinib for fractionated radiotherapy and stereotactic radiosurgery before and after radiotherapy as outlined below ([Anker CJ et al, 2016](#)).
 - Interrupt dabrafenib and trametinib ≥ 3 days before and after fractionated radiation
 - Interrupt dabrafenib and trametinib ≥ 1 day before and after stereotactic radiosurgery (SRS)
- Inactivated vaccines.
- The subject must be told to notify the investigational site about any new medications he/she takes after the start of the study drug. All medications (other than study drug) and significant non-drug therapies (including physical therapy, herbal/natural medications and blood transfusions) administered during the study must be listed on the Concomitant Medications or the Procedures and Surgical and Medical Procedures eCRF.

